# 7.7.1.4 Analysis of superiority to placebo

The analysis of superiority will be performed separately for the Test treatment versus the Placebo and for the Reference treatment versus the Placebo. Each of these analyses will be performed as follows:

2. Superiority will be declared if the Test and Reference LS means are each greater than the Placebo LS mean and the respective p-values are < 0.05.

Analysis of superiority will be performed on the mITT set.

# 7.8 Safety Analyses

All safety analyses will be performed on the SAF. Additionally some analysis of safety in the Run-in period will be performed on the Run-in Failure Set.

#### 7.8.1 Adverse Events

Adverse Events will be coded using the Medical Dictionary of Regulatory Activities (MedDRA Version 22.0) AE coding system for purposes of summarization.

An AE will be considered as study-emergent if the date of onset is on or after the date of informed consent.

An AE will be considered as treatment-emergent if the time of onset is on or after the time of the first randomized study drug administration in the Treatment period. AEs with unknown start dates will be counted as treatment-emergent unless the AE resolution date is prior to the randomized drug start date. If the start date is partially missing, the AE will be considered treatment-emergent, unless the month and year (when available) rule out the possibility that the event occurred post start of randomized dosing.

A TEAE is defined as treatment-related if its relationship to study medication is recorded as "reasonable possibility" on the eCRF. In case the relatedness was not assessed, the most conservative result (related) will be chosen for the analysis.

In summaries of TEAEs a subject experiencing the same AE multiple times will only be counted once for that preferred term. Similarly, if a subject experiences multiple AEs within the same system organ class that subject will be counted only once in that system organ class. When summarizing AEs by severity, only the most severe occurrence within the preferred term or system organ class will be used. Similarly, when summarizing AEs by relationship to study drug, only the most related occurrence within the preferred term or system organ class will be selected for displays in summary tables.

An overall summary for the SAF will include, by treatment group and overall, the number and percentage of subjects reporting at least 1 TEAE in the following categories:

- Any TEAE
- Treatment-related TEAE

- Serious TEAE
- TEAE leading to discontinuation of the study medication
- TEAE leading to death.

The following TEAE frequency tables will be prepared summarizing the overall number of TEAEs, the number and percentage of subjects reporting at least one TEAE by MedDRA System Organ Class (SOC) and preferred term (PT), by treatment group for the SAF:

- All TEAEs
- Serious TEAEs
- Treatment-related TEAEs
- AEs leading to discontinuation of the study medication
- TEAEs by Severity
- TEAEs by Relationship to Study Medication.

Additionally, the following summaries of the study-emergent AEs that are not treatmentemergent (i.e. occurred in the Run-in period) will be presented for the Run-in Failure Set:

- Overall summary similar to the overall summary of TEAEs
- AEs by System Organ Class and Preferred Term

All information pertaining to adverse events noted during the study will be listed by subject, detailing verbatim, preferred term, system organ class, start date, stop date, intensity, outcome, action taken and causal relationship to the study drug. The adverse event onset will also be shown relative (in number of days) to the date of first administration of the study medication. In addition the adverse event duration (if AE Stop Date is available) will be evaluated as below and presented (in number of days).

AEs occurring in the Run-in period will be listed separately from the TEAEs.

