#### 3. STUDY OVERVIEW

### 3.1 Study Design

This is a multicenter, blinded, parallel group, placebo-controlled, randomized, multiple dose clinical study designed to confirm therapeutic equivalence of FP pMDI 110 mcg per actuation and Flovent HFA 110 mcg in adult subjects with asthma.

The Screening and Run-in study periods and visit windows described in this section may be extended with Sponsor approval. The Treatment period may not be extended.

The Screening period will have up to 2 visits. Screening Visit 1a may be conducted up to 28 days prior to Visit 1b. At Visit 1a subjects will provide written informed consent, demographics, medical history, and concomitant medication information. Subjects will receive rescue medication for the duration of the study. Subjects' height and weight will be measured and BMI will be calculated. Subjects must withhold rescue medication for 6 hours prior to performing any spirometry. If all protocol-defined washout requirements are met, Visit 1a and 1b may be combined and conducted on the same day.

At Screening Visit 1b, subjects will perform Screening spirometry with reversibility. Prebronchodilator FEV1 must be  $\geq$ 45% and  $\leq$ 85% of predicted normal value at Screening Visit 1b using NHANES III predicted values. For Screening Visit 1b only, subjects who fail to meet FEV1  $\geq$ 45% and  $\leq$ 85% of predicted normal value may repeat the visit one time within 1 week. Subjects must demonstrate reversibility of airway obstruction  $\geq$ 12% and  $\geq$ 200 mL of FEV1 within 30 minutes of 360 mcg albuterol inhalation (4 puffs). Subjects who achieve  $\geq$ 10% but <12% or achieve  $\geq$ 12% but 175-199 mL reversibility at Screening Visit 1b may repeat the visit one time within 1 week. Subjects may have only one repeated visit during the Screening period.

Vital signs will be collected at all clinic visits after Screening Visit 1a (blood pressure and heart rate). Physical examination, urinalysis, drug/alcohol/cotinine screening, laboratory screening (blood: hematology, chemistry), and urine pregnancy test (women of childbearing potential only) will be conducted at Screening Visit 1b. A 12-lead ECG will be collected. Subjects must have no evidence or history of clinically significant disease such as congestive heart failure, myocardial infarction, or cardiac dysrhythmia.

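### The partial-start-date rule for AEs ignores the resolution date, so an event that ended before the first randomised dose can be counted as treatment-emergent

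*SAP*

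**What the plan says.** SAP section 7.8.1 (Adverse Events) classifies AEs in three successive steps.

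1. **Definition.** An AE is treatment-emergent "if the time of onset is on or after the time of the first randomized study drug administration in the Treatment period".
2. **Wholly unknown start date.** "AEs with unknown start dates will be counted as treatment-emergent unless the AE resolution date is prior to the randomized drug start date".
3. **Start date known only in part.** "If the start date is partially missing, the AE will be considered treatment-emergent, unless the month and year (when available) rule out the possibility"; what has to be ruled out is onset after randomised dosing began.

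The same section counts AEs from consent ("An AE will be considered as study-emergent if the date of onset is on or after the date of informed consent"). It states that "AEs occurring in the Run-in period will be listed separately from the TEAEs". The AE listing includes the stop date ("detailing verbatim, preferred term, system organ class, start date, stop date, intensity, outcome").

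**The concern.** The resolution date is a ground for exclusion only in the second step. In the third step the only ground is the month and year of onset. That handles an onset month before the dosing month, or a year-only date before the dosing year. It fails when the known parts of the start date are compatible with onset after dosing but the stop date is not. An event that ended before the first randomised dose cannot have begun on or after it, so in these cases the third step contradicts the definition in the first.

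The result is also perverse: knowing the month of onset gives the wrong class, while knowing nothing about onset gives the right one.

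A misclassified AE would enter the by-arm TEAE tables and be listed with the TEAEs instead of with the run-in events. If its relatedness was not assessed, the section's default would also count it as treatment-related.

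**Working it through.** The SAP gives no figure to reproduce here. The check applies the three rules literally, first to one case and then across a calendar year.

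**One event, four levels of start-date information.** First randomised dose 20 June 2019; AE resolved 12 June 2019.

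| Recorded start | Rule that applies | Result |
|---|---|---|
| 8 June 2019 | definition | not a TEAE |
| June 2019 | partial date; same month and year as dose, so not ruled out | TEAE |
| 2019 | partial date; same year as dose, so not ruled out | TEAE |
| unknown | resolution date before dose | not a TEAE |

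**How often the partial-date rule fails.** The set considered is narrow: AEs that began and ended before the first dose, with a partial start date and a known stop date.

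Inputs from SAP section 3.1:
- The run-in lasts at least 14 days.
- "Screening Visit 1a may be conducted up to 28 days prior to Visit 1b".
- "The Screening and Run-in study periods and visit windows described in this section may be extended with Sponsor approval".

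Because AEs count from consent, the pre-dose window can reach 28 + 14 = 42 days with a minimum run-in. It reaches 28 + 28 = 56 days if a 28-day run-in is assumed.

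Assumptions not in the SAP:
- The first dose is equally likely on each of the 365 days of 2019.
- Onset is uniform over the pre-dose window.
- The AE resolves k days after onset, with k from 0 to 5.

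Method: for window length L, onset falls d days before the dose, with d = k+1, …, L, so that the stop date precedes the dose. The number of cases is 365 × (L − k). A case is misclassified under a month-year start date if onset falls in the same month and year as the dose. Under a year-only start date it is misclassified if onset falls in the same year.

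| L (days) | Month-year, k = 0 | Month-year, k = 5 | Year only, k = 0 | Year only, k = 5 |
|---|---|---|---|---|
| 14 | 3850/5110 = 75.3% | 2205/3285 = 67.1% | 5005/5110 = 97.9% | 3195/3285 = 97.3% |
| 21 | 4893/7665 = 63.8% | 3248/5840 = 55.6% | 7434/7665 = 97.0% | 5624/5840 = 96.3% |
| 28 | 5348/10220 = 52.3% | 3703/8395 = 44.1% | 9814/10220 = 96.0% | 8004/8395 = 95.3% |
| 42 | 5373/15330 = 35.0% | 3728/13505 = 27.6% | 14427/15330 = 94.1% | 12617/13505 = 93.4% |
| 56 | 5373/20440 = 26.3% | 3728/18615 = 20.0% | 18844/20440 = 92.2% | 17034/18615 = 91.5% |

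**Sensitivity to AE duration.** Longer events must start further back, so fewer share the dosing month. Month-year shares become:
- L = 42, k = 14: 1523/10220 = 15%
- L = 56, k = 14: 1523/15330 = 10%
- L = 56, k = 21: 480/12775 = 4%
- L = 56, k = 30: 0%

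**After the fix.** With the resolution-date exception also applied to partial start dates, 0 of the 5110 cases (L = 14, k = 0) are TEAEs, for month-year and year-only dates alike. Complete and wholly unknown start dates already give 0 of 5110.

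**The case against.** The best defence is that a start date lacking its day is itself an unknown start date. The resolution-date exception would then already cover it, and the next sentence would only add a second ground for exclusion. That reading is possible but does not fit the text well: partial dates have their own sentence, with a different exception. Even if it is accepted, an AE with a partial start date and an early stop date falls under two sentences that give opposite answers, so the wording still needs repair.

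The second argument is rarity, and it largely stands. From the start of run-in, subjects report health changes in a daily eDiary, and interim history including AEs is reviewed at Visit 2 before dosing. A start date with an unknown day and a known early stop date should be uncommon, and a year-only date for an AE that began after consent more so. AEs between consent and run-in have less of this protection.

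The third argument is that the percentages rest on assumed dates and durations. This also stands: 20% is not a lower bound once AEs last longer than five days.

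Finally, the error is conservative, and because these events precede randomised treatment they should fall on the arms without regard to it. The planned summaries of run-in AEs cover only the Run-in Failure Set, whose members received no randomised drug, so they are untouched. All of this limits the importance of the point. It does not make the rule correct: conservatism is a reason to resolve uncertainty towards TEAE, and here the stop date leaves no uncertainty.

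**Conclusion.** The concern holds. As written, the partial-date rule in section 7.8.1 classes some AEs that demonstrably ended before randomised dosing as treatment-emergent. This conflicts with the section's own definition, with its handling of unknown start dates, and with its separate listing of run-in AEs.

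Within the narrow set of affected AEs, about 20–75% of month-year cases and about 92–98% of year-only cases would be misclassified, given a 14- to 56-day window, uniform onset and resolution within five days. A longer window or longer-lasting AEs would lower these shares. The SAP does not indicate how many such AEs to expect; the number is probably small, and the shares do not measure the effect on any TEAE table.

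The consequence is confined to descriptive safety outputs and can only inflate TEAE counts. The equivalence and superiority analyses are not affected. This is a minor correction worth making before unblinding, so that the derivation is not left to the programmer's judgement.

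**What to change.** In section 7.8.1, add a second ground for exclusion to the partial-start-date sentence: the AE is also not treatment-emergent if its resolution date is before the start date of randomised drug. This is the condition the SAP already uses for unknown start dates. It removes no AE that could have begun after dosing, and an AE without a resolution date stays treatment-emergent as now.

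The cost is one clause in the SAP and one line of derivation code. The stop date is already among the AE data to be listed, so nothing new has to be collected.

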# 7.8.2 Laboratory tests

Laboratory safety assessment (i.e., clinical chemistry, hematology, urinalysis) will be assessed by investigators for the presence of any findings that meet the description of an AE. Laboratory test results will not be listed or summarized.

Pregnancy test results and results of the drug, alcohol and cotinine screen will be listed.

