At the end of the Run-in period subjects will be randomized to treatment if they continue to meet all general Inclusion/Exclusion criteria. In addition, they must meet all randomization inclusion criteria and no randomization exclusion criteria specified in the protocol.

Eligible, randomized subjects will receive the first dose of study medication following serial spirometry at Visit 2 Randomization. Subjects will receive blinded study medication with instructions for home for the minimum 28 day () Treatment period. Subjects will be instructed to take two oral inhalations twice daily, with a dosing interval of approximately 12 hours.

Subjects will review eDiary requirements and instructions for use of diary at home, and will complete the first diary entries at the clinic under site staff supervision. Subjects will be instructed to record eDiary twice-daily (morning and evening) entries for study drug dosing and peak flows. Once-daily (morning) entries for rescue medication use, asthma symptoms, and reporting health and medication changes will also be recorded. Subjects will be instructed to withhold their morning medication (last dose should be approximately 12 hours prior to lung function tests), as well as rescue medication for 6 hours, on the day of Visit 3 Day 29.

[figure not shown]
Medication and eDiary compliance will be monitored throughout the Run-in and Treatment period, beginning when the eDiary/PEF device is dispensed. Compliance monitoring will include alerts, edit checks, and data management review. Sites will contact subjects as needed to follow-up on diary and medication compliance alerts.

Subjects will return to the clinic for Visit 3 Day 29 at the end of the minimum 28 day

Treatment period. The subject's interim medical history (including AEs) and required medication washout will be reviewed. Washout for Treatment medication must be observed for a minimum of 6 hours on Visit 3 Day 29. Subject must withhold rescue medication for 6 hours prior to spirometry on the day of Visit 3 Day 29. Laboratory screening (blood: hematology, chemistry) will be conducted. Urine pregnancy tests will be conducted for women of childbearing potential. The subject's Diary and medication compliance will be reviewed.

Subjects will perform serial spirometry over approximately 60 minutes, subjects will be required to perform three separate sessions of spirometry, allowing adequate time for subject

recovery between sessions.  1. Sites will

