#### 7. STATISTICAL METHODS OF ANALYSIS

# 7.1 General Principles

The statistical analyses will be performed by \_\_\_\_\_, with approval of the Sponsor, using SAS Version 9.4 (or higher). All tables, figures and listings will be produced in landscape format.

In general, all data will be listed by subject and visit/time point where appropriate. The summary tables will be stratified by, or have columns corresponding to, treatment groups.

The total number of subjects in the treatment group (N) under the specified analysis set will be displayed in the header of summary tables.

Data will be summarized using descriptive statistics for continuous variables. Unless otherwise specified, descriptive statistics will include number of subjects, mean, standard deviation, minimum, median and maximum. Number of subjects with missing values will also be displayed, but only if non-zero. The minimum and maximum statistics will be presented to the same number of decimal places as the original data. The mean and median will be presented to one more decimal place than the original data. The standard deviation will be presented to two more decimal places than the original data.

In summary tables of categorical variables, counts and percentages will be displayed. The count [n] indicates the actual number of subjects in a particular category, which should always be less than or equal to the total number of subjects in the respective study group with known (non-missing) category [M]. Percentage will be obtained by: % = n/M\*100. Unless otherwise specified, all percentages will be expressed to one decimal place.

All statistical tests will be two-sided at a significance level of  $\alpha = 0.05$ , unless otherwise indicated. No adjustment will be made for multiplicity.

Baseline will be defined as the last assessment, scheduled or not, prior to the first dose of the randomized study drug, unless otherwise specified.

In by-visit summaries, only data collected on scheduled visits/timepoints will be summarized. Data from unscheduled assessments will be included in listings and may be used in determination of baseline if applicable.

Relative days will be calculated relative to date of first dose of randomized study medication. Relative days will be calculated as follows only when the full assessment date is known (i.e., partial dates will have missing relative days).

For assessment on or after the day of first dose of the randomized study drug:

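### Hematology and chemistry results will be neither listed nor summarised, so laboratory safety reaches the treatment comparison only through findings that investigators report as adverse events

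*SAP*

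**What the plan says.** **Sampling.** SAP section 3.1 places the first blood panel at Screening Visit 1b, in a list that reads "Physical examination, urinalysis, drug/alcohol/cotinine screening, laboratory screening (blood: hematology, chemistry), and urine pregnancy test". For Visit 3 (Day 29), and again for the Early Termination visit, the same section states: "Laboratory screening (blood: hematology, chemistry) will be conducted". Urinalysis is described only at Visit 1b.

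**Use of the results.** Section 7.8.2 says that laboratory assessments "will be assessed by investigators for the presence of any findings that meet the description of an AE". It then rules out any other output: "Laboratory test results will not be listed or summarized". The same section makes a separate provision for other tests: "Pregnancy test results and results of the drug, alcohol and cotinine screen will be listed".

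**The general rule.** Section 7.1 says: "In general, all data will be listed by subject and visit/time point where appropriate".

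**The adverse-event route.** Section 7.8.1 tabulates treatment-emergent events "by MedDRA System Organ Class (SOC) and preferred term (PT), by treatment group for the SAF", and adds: "All information pertaining to adverse events noted during the study will be listed by subject".

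**The concern.** The plan collects hematology and chemistry before and after randomized treatment in all three arms, then leaves the results out of every table and listing. What remains is a yes-or-no judgement by an investigator, one subject at a time, on whether a result amounts to an adverse event.

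That filter can pass over two kinds of information. One is a modest movement of a laboratory value across an arm, where no single result is remarkable. The other is a difference between arms in how often results fall outside the normal range, where the individual results are not reported as events. A reader of the study report would see neither. Nor could the reader check, from the planned outputs, whether the adverse-event judgement was applied evenly, because the results behind it are not shown.

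What is at stake is the completeness of the safety description of Test against Reference and placebo. The FEV1 conclusions are not involved.

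**Working it through.** No arithmetic applies. The point rests on no sample size, power, error rate or event count, and the plan gives no figure to reproduce. The check follows each kind of safety data from collection (section 3.1 and the subsections of 7.8) to planned output (7.8.1 to 7.8.6).

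| Data | When collected | Listed? | Shown by treatment group? |
|---|---|---|---|
| Adverse events | From consent | Yes | Yes, for treatment-emergent events |
| Vital signs | Visits 1b, 2, 3, early termination | Yes | Yes, with change from baseline at Visit 3 |
| 12-lead ECG | Visit 1b | Yes | No |
| Physical examination | Visit 1b | Yes | No |
| Drug, alcohol and cotinine screen | Visit 1b | Yes | No |
| Pregnancy test | Visits 1b, 2, 3, early termination | Yes | No |
| Diary peak flow | Run-in and Treatment | Yes | Yes, plotted |
| Urinalysis | Visit 1b | No | No |
| **Hematology and chemistry** | **Visits 1b, 3, early termination** | **No** | **No** |

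Four things follow.

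1. Hematology and chemistry are the only laboratory safety panels that section 3.1 describes after randomized dosing. Each subject has at most one such scheduled occasion: Day 29, or early termination for those who withdraw.
2. No planned output shows their values, out-of-range results or shifts, by subject or by arm.
3. One indirect route is open. A finding with onset after the first randomized dose that is reported as an adverse event enters the by-arm tables and the by-subject listing in 7.8.1.
4. The treatment of these data differs from its neighbours. ECG, physical examination and the drug screen are done only before randomization and cannot show a treatment effect, yet they are listed. Vital signs, also measured before and after treatment, are both listed and summarised by arm. Section 7.8.2 gives no reason for handling the blood panels otherwise.

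On consistency with section 7.1: the listing rule there is qualified twice, once as a general statement and once by appropriateness. A specific section may make an exception to such a rule. Section 7.8.2 does so openly, but does not explain why listing would be inappropriate here.

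**The case against.** The best case for the plan is that this is a stated choice. Section 7.8.2 says how laboratory results are used and what will not be produced, and the qualified rule in 7.1 leaves room for that. This stands: a reader might infer that the SAP contradicts itself, and it does not.

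A reader might also infer that the arms cannot be compared on laboratory safety at all. The documents do not support that, because findings reported as adverse events are tabulated by treatment group and listed. The loss is confined to what stays below that threshold.

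Three further inferences lack a source:

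- **Purpose of the samples.** Nothing says the blood is drawn for a comparison between arms. Section 3.1 calls it screening at each visit, and the only stated use is review for adverse events.
- **Reporting thresholds.** The SAP does not say that they differ between sites. The study is multicenter, but the definition of an adverse event would sit in the protocol, which is not at hand.
- **The equivalence claim.** Neither objective in section 2 concerns safety, and equivalence is defined by the FEV1 ratio alone. A missing laboratory table does not weaken that conclusion.

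The protocol may also set or justify the same handling, since section 8 reports no change from the protocol's analyses. That cannot be checked here. It might supply a reason, but it would not put the results into any SAP output.

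None of this removes the core point: an explicit rule, given without a reason, keeps safety data that are already being collected out of every table and listing.

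**Conclusion.** The point holds as a minor one about safety reporting. Laboratory safety enters the Test, Reference and placebo comparison only through investigator-reported adverse events. Hematology and chemistry values, out-of-range rates and shifts below that threshold appear nowhere.

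Its reach is every dosed subject with a Visit 1b sample and a Visit 3 or early-termination sample. No subject count can be attached, because the sample-size text is not legible in the public copy. This measures how much data goes unreported. It is not evidence that a safety signal has been missed, and the equivalence and superiority analyses are untouched.

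The conclusion assumes that the visit descriptions in section 3.1 give the full laboratory schedule (the appendix with the schedule of procedures is not in the copy at hand) and that the separate table and listing shells follow section 7.8.2.

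**What to change.** Replace the sentence in section 7.8.2 with text to this effect:

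> Hematology and chemistry results will be listed by subject and visit, with values outside the reference range flagged. A normal-range shift table from Visit 1b to the post-treatment sample (Visit 3, or early termination for subjects who withdraw), or a summary of change from Visit 1b, will be presented by treatment group for the SAF.

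Naming the early-termination sample matters, because otherwise subjects who withdraw could drop out of a table limited to Visit 3. If the sponsor prefers to keep the present rule, the SAP should state the reason.

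The cost is one listing and one or two tables. If the study database does not already hold the results, they must be transferred with units and reference ranges. The SAP does not say whether they are held there or whether the laboratory is central or local, so the size of that task is unknown. No new samples or subjects are needed, and nothing in the efficacy analysis changes.
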